2.2.1.2 Secondary efficacy endpoint(s)

All time to event endpoints are measured from date of randomization. It is expected that there will be approximately 24 hours between randomization and dosing.

All endpoints associated with each secondary objective are listed together. The key endpoints are written in bold to be analysed/summarized at the second interim analysis when all participants have had the opportunity to complete Day 28 Procedures. Collected endpoints and their timing that may be used to derive the endpoints are listed in the third column. Alternative sources of the same information may be available and used.

There is overlap on some of the measurements across endpoints. Some may be taken once for each endpoint or taken once and used for more than one endpoint.

Details of the items in the 6-point ordinal score are provided below this table. Brief details of SOFA, are provided and further information can be obtained from the hyperlink.

Secondary Objective	Endpoint	Measurement

1) To study if early intervention with Zilucoplan® affects clinical outcome defined by duration of hospital stay, 6-point ordinal scale, time to defervescence, supplemental oxygen use, SOFA score
	
Incidents of participants reporting each severity rating in 6-point ordinal scale at D1, D6, D15 and D28
 
Change from baseline in 6-point ordinal scale to Day 6, Day 15 and Day 28 (by phone call) weeks post randomisation
 
Time to at least a 2-point improvement or discharge sustained up to D28 on the 6-point ordinal scale during 28-day assessment period
 
Percentage of participants reporting at least a 2-point improvement sustained to D28 or discharge
 
AUEC/Time using the 6-point score recorded daily – up to D15, D28 and all data recorded
 
Percentage of participants who record a 2-point improvement from baseline or discharge at D6, D15 and D28
 
Percentage of participants not deteriorating according to the ordinal scale by 1 or 2 points on D6, D15 and D28
 
6-point ordinal Scale at D6 and D15 and D28 in relation to D-Dimers and complement C5a levels at baseline
	
6-point ordinal scale measured daily up to discharge, D28 and follow-up
 
Lab values at baseline for D-Dimers and C5a

	
Change from baseline in SOFA score (https://www.mdcalc.com/sequential-organ-failure-assessment-sofa-score) to Day 6, Day 15 (or at discharge, whichever comes first)
	
SOFA score measured at D1, D6 and D15

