3.6.2 Change of Centres

Due to the ongoing pandemic participants may be required to move hospitals. No IMP will move with the participants and hence dosing will stop. Prophylactic antibiotic use will continue where appropriate.

If participants are moved to a hospital within the study then safety (conmeds, AEs, labs and temperature) and key efficacy data (primary oxygenation endpoint, ordinal scale, respiration data and mortality) will be prioritised.

If participants are moved to a hospital outside the conduct of the study then only key safety data (conmeds, AEs, SAEs) will be collected.

Centre changes will be captured and reported as well as day of transfer. Data collected for participants after transfer to another hospital may not be included in any formal analyses, but will be listed.

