4.2 Handling of dropouts or missing data

The SOE indicates some endpoints are listed as only being collected on the specified days where comparisons between treatments are required, but all clinical and laboratory endpoints will be collected as frequently as possible, preferably daily, whilst in hospital. The primary assessment period is for 28 days post randomization, but some endpoints cannot be collected once a participant has been discharged from hospital e.g. vital signs (including the primary endpoints) and laboratory endpoints.

See Section 5.1 for definitions for Completed Treatment and Completed Study and their complements.

Missing values from participants take 4 forms:

- Missing due to death (no longer 'at risk' of recovery)
- Missing due to hospital discharge prior to end of primary assessment period (on any day up to D28)
- Missing values from the ideal of having daily collection of laboratory and clinical endpoints whilst participants are in hospital
- Missing values due to premature withdrawal from study

How missing data are to be handled is described in the analysis sections for each endpoint.

Participants who discontinue *study treatment* for reasons other than death or hospital discharge (for example, withdraw consent or adverse event, may still continue on study and will have measurements taken, so data from timepoints following discontinuation from *study treatment* will not be missing. These participants/data may be considered differently as part of a sensitivity analysis as they did not receive treatment per protocol.

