5 STUDY POPULATION CHARACTERISTICS

5.1 Participant disposition

Participants are considered **screenfails** if they were deemed not eligible for randomisation.

Since this is initially an in participant study the Nominal Days are not considered a scheduled protocol visit.

A participant who dies at any time during the study is considered as having **completed the study and primary assessment period**. If they discontinued early from planned active treatment duration (i.e. not including hospital discharge), the participant is considered as having **completed the study and primary assessment period, but not completed planned active treatment duration**.

In addition, a participant is considered to have **completed the study** if they have completed D28 and the follow-up visit. Participants can be discharged from hospital at any time, and as long as they have completed D28 and the follow-up visit, they have **completed the study**.

Participants have **completed primary assessment period** if they have:

- Arm A: completed up to 14 days of treatment with study drug followed by 14 days of either IV or oral prophylactic antibiotic treatment (as an in-participant or after discharge from hospital) AND completed D28 procedures
- Arm B: Completed up to 14 days of treatment with study drug (SOC+ 1 week of prophylactic antibiotic treatment) AND completed D28 procedures

Participants have **not completed primary assessment period**:

- are discontinued treatment prior to end of planned active treatment duration due to an adverse event - they may still complete D28 and/or follow-up visits
- discontinue treatment prior to end of planned active treatment duration as they meet an exclusion criterion (either newly developed or not previously recognized) that precludes further study treatment participation - they still may complete D28 and/or follow-up visits
- withdraw consent from being treated prior to end of planned active treatment duration – they may agree to complete D28 and/or follow-up visits
- Complete the treatment as planned but do not complete D28 procedures

Participants have prematurely **withdrawn from the study** if they:

- are lost to follow-up, after hospital discharge (i.e. do not complete D28 and follow-up visits or do not complete follow-up visit).
- Withdraw consent from being treated prior to end of planned active treatment duration and from D28 and follow-up visits

-

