
Objective 2
 
Change from baseline in 6-point ordinal scale to Day 6, Day 15 and Day 28
	
Change from baseline at each relative day for each participant. If a participant has died (score=1) or discharged from hospital (score=6), these values will carry forward onto subsequent days. For participants who are missing values after any day for any other reason, the value will remain missing. For participants who miss some intermediate values, the latest value prior to the missing value will be carried forward until the day where data are recorded again.
 
The additional scores derived for the previous endpoint will not be used in change from baseline
 
(One line per day per participant dataset)
	
Summary table providing n, mean change from baseline, SD change from baseline, median, minimum and maximum on each specified nominal day by treatment arm
 
Graph of change from baseline over time for each participant by treatment, and the average lines for each treatment.
 
For final analysis: MMRM fitting response variable change from baseline against fixed effects for specified nominal days, treatment and treatment*nominal day interaction. Baseline score as covariate and baseline score*nominal day as additional terms. Participant as random effect.

Objective 2
 
Time to at least a 2-point improvement or discharge sustained up to (D15 for interim analysis 1) D28 on the 6-point ordinal scale during 28-day assessment period (=Response)
 
Note: for both the interim analyses and final analyses up to D15 and D28 respectively, if the 2-point change occurred on D15 or D28, and the
	
Create TTE dataset for cumulative response rate analysis with 2 variables each for analysis up to D15 and up to D28 with one line per participant providing time to response and censor status. Censor status=0 for patients with response and =1 on relative day for: patients who have: withdrawn from treatment and/or study; discharged from first hospital for reasons other than improvement; have no response by analysis date (censor=1 at analysis
	
Kaplan-Meier analysis using PROC LIFETEST. Strata ACTARM.
 
Request Failure plot adjusting axis and heading titles to reflect responder and not failure
 
Output statistics:
 
Appropriate statistics from analysis as indicated in mock shell

Endpoint	Derivation	Analysis

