
patient remained in hospital, the patient will be classified as a responder, even though the 2-point change had not been ‘sustained’.
	
date). If Time to Response >15 and censor=1 for analysis up to D15, Time to Response=15. If Time to Response >28 and censor=1 for analysis up to D28, Time to Response=28. For patients who have died Time to Response is set to D15 or D28 respectively and censored at this time. Note: Treatment will be merged into the TTE dataset. In addition to other variables that may be used as covariates in final analysis.
 
(one line per participant dataset)
	

Objective 2 Percentage of participants reporting at least a 2-point improvement sustained to D28 or discharge
	
Use D28 response indicator variable defined above
	
PROC FREQ/PROC LOGISTIC(if covariates are added) Model: Response=ACTARM +covariates (if added) Output percentage response on each treatment. Odds ratio and 95% confidence interval

Objective 2 AUEC/Time using the 6-point score recorded daily – up to D15, D28 and all data recorded
	
For each participant calculate the area under the curve and divide by 15 for up to D15 and by 28 for up to D28 (higher average score per day the better the response). Use last value brought forward for any missing values until next data entry. For discharge, carry forward score=6 for each day post discharge day. For death, carry forward score=1 for each day post death day.
	
Analyse AUEC/Time using analysis of variance with ACTARM as a two-level factor and baseline score as a covariate

Endpoint	Derivation	Analysis

Objective 2 Percentage of participants who record at least 2-point improvement from baseline or discharge (response) between D1-D6, D7-D15 and D16-D28
	
Responder classified as above. Create indicator variable (3 levels) if the relative day of START of response is between D1 and D6, between D7 and D15 or between D16 and D28. Each responder participant can only be within one of these categories. Participants who have a missing value are classified as non-responders
	
Frequency table and percentage responders in each of the categories defined by the indicator variable, by treatment. Exact 95% confidence intervals for each percentage

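### Censoring time to sustained 2-point improvement when study treatment stops discards outcome data the plan expects to hold, and may bias the response curve

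*SAP*

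**What the plan says.** SAP Table 8.1 (section 8.2) gives responders censor status 0. It gives status 1, on the relative day, to patients who have "withdrawn from treatment and/or study; discharged from first hospital for reasons other than improvement", and to those with no response by the analysis date. The analysis is "Kaplan-Meier analysis using PROC LIFETEST. Strata ACTARM", plotted as cumulative response.

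The same table treats deaths differently: "For patients who have died Time to Response is set to D15 or D28 respectively and censored at this time". The endpoint for the percentage with a sustained 2-point improvement reuses the D28 response indicator from this dataset.

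On follow-up, SAP 4.2 says that patients who stop study treatment for reasons other than death or discharge "may still continue on study and will have measurements taken", so their later data are not counted as missing. SAP 5.1 says of those stopping for an adverse event that "they may still complete D28 and/or follow-up visits", and says much the same of those who newly meet an exclusion criterion. The data source in SAP 2.2.1.2 is the "6-point ordinal scale measured daily up to discharge, D28 and follow-up".

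**The concern.** A patient who stops the drug on day 5 but is scored daily and reached at D28 has a known outcome. The rule replaces it with the Kaplan-Meier assumption that this patient would have responded like those still at risk.

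That assumption is doubtful, given the reasons for stopping that the documents list. Protocol 8.1.4 interrupts the drug for anaphylaxis or a severe adverse event. Protocol 7.1.2 adds newly met exclusion criteria, which under protocol 6.2 include active bacterial or fungal infection, low platelets or neutrophils, and being unlikely to survive 48 hours.

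The endpoint matters for decisions. Protocol 4.2 keeps it as a secondary endpoint. SAP 4.4 schedules it for Interim 2, which may serve as the final analysis of key secondary endpoints and guide further research, and allows it at Interim 1. Because SAP 3.1 gives no p-values for secondary endpoints, the estimate and its interval are the evidence.

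**Working it through.** **Figures in the plan.** None is stated for this endpoint. The dropout rate of less than 10% in SAP 2.4 belongs to the power calculation for PaO2/FiO2 and is not a treatment-stopping rate. All rates below are assumptions, except the 54 patients in Arm A.

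**1. Worked example.** Take 54 patients in Arm A, of whom 38 respond at even spacing over days 3 to 27. With everyone followed to D28, response is 38/54 = 70.4%. Let k of the 16 non-responders stop on day 5 and be censored then. Four patients have responded by day 5, so 50 - k remain at risk afterwards and 16 - k never respond:

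Kaplan-Meier response at D28 = 1 - (50/54) × (16 - k)/(50 - k)

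- k = 3: 1 - (50/54)(13/47) = 74.4%
- k = 5: 1 - (50/54)(11/45) = 77.4%
- k = 8: 1 - (50/54)(8/42) = 82.4%

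**2. Dependence on prognosis.** Assume a constant daily response hazard h with 1 - (1 - h)^28 = 0.70, so h = 1 - 0.30^(1/28) = 0.042. Ten percent of patients are assigned a stop day, uniform on days 2 to 10; about 7.8% stop before responding. After the stop the hazard is r × h. Table 8.1 can be read in two ways:

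- Reading 1: every stopper is censored at the stop, whatever follows.
- Reading 2: a patient who ever responds keeps status 0, so only non-responding stoppers are censored at the stop.

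Simulation with 400,000 patients per setting gives, in percent at D28:

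| r | True response | Kaplan-Meier, reading 1 | Bias | Kaplan-Meier, reading 2 | Bias | Binary responder rate, reading 1 |
|---|---|---|---|---|---|---|
| 0 | 65.3 | 70.1 | +4.8 | 70.1 | +4.8 | 65.3 |
| 0.5 | 68.2 | 70.0 | +1.8 | 71.2 | +3.0 | 65.2 |
| 1 | 69.9 | 69.9 | 0.0 | 71.8 | +1.9 | 65.2 |
| 1.5 | 71.2 | 70.1 | -1.1 | 72.4 | +1.2 | 65.3 |

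The first row can be checked by hand. The mean of 0.30^(s/28) over s = 2 to 10 is 0.777, so true response is 0.9 × 0.70 + 0.1 × (1 - 0.777) = 65.2%, against 70% from the censored curve.

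**3. Wider ranges.** Response was varied over 50, 70 and 80%, and stopping over 5, 10 and 20%. Under reading 1 the bias runs from +0.8 to +10.2 points for r = 0 or 0.5, is about 0 for r = 1, and is -0.5 to -2.4 points for r = 1.5. Under reading 2 it is upward throughout, from +0.4 to +10.2 points, even at equal prognosis, because the rule then removes only stoppers known not to respond.

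**4. The binary endpoint.** Under reading 1, stoppers who respond later count as non-responders. At r = 1 the rate is 65.2% against a true 69.9%, an error of about 5 points against whichever arm has more stoppers. Under reading 2 this error disappears.

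**5. Deaths.** A patient who stops treatment and then dies meets two rules: censor at the stop, or keep at risk to D15 or D28. No order is stated.

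**The case against.** A reader might infer that the rule inflates the zilucoplan curve as a matter of fact. The documents do not support that. They say nothing about the prognosis of stoppers. If all stoppers are censored, the bias vanishes at equal prognosis and reverses if they do better. It is upward in every scenario examined only if responders always keep status 0.

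Nor do the documents show that the effect falls mainly on Arm A. SAP 3.2.1.2 sets a planned treatment period of D1 to D14 for both arms, and the censoring rule names no arm. More stopping in Arm A is a reasonable inference, since it has a daily injected drug for up to 14 days against one week of antibiotic in Arm B. No between-arm bias was calculated.

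Further points stand in part:

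- If the death rule takes precedence, stoppers who die stay at risk, which removes the most obvious source of upward bias.
- Follow-up after stopping is something patients *may* continue. Protocol 7.1.2 speaks of discontinuing or withdrawing a subject from the study, so some stoppers may leave altogether.
- Change from baseline and AUEC/Time on the same scale do not cut off at treatment stop, so the later course is not lost from the plan.
- SAP 4.2 allows a sensitivity analysis for stoppers, but it is optional and not specified for this endpoint.
- A bias of 2 to 5 points is below one standard error for 54 patients, √(0.7 × 0.3/54) = 6.2 points. The 95% half-width for 54 against 27 is 1.96 × √(0.21/54 + 0.21/27) = 21 points. SAP 4.5 calls the secondary hypotheses exploratory.

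None of this justifies discarding scores that are scheduled and, for patients who stay, collected.

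**Conclusion.** The point holds as a possible bias. The plan censors at treatment withdrawal while expecting many of the same patients to be measured to D28, and this conflicts with its own handling of deaths and of the other ordinal endpoints. The most plausible direction is upward, more so in Arm A, but neither direction nor size can be settled from the documents. With 70% response and 10% stopping assumed, the bias under reading 1 ranges from about +5 to -1 points. The companion responder rate could err the other way, against the drug.

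The primary analysis is unaffected. The correction is worth making before database lock because this secondary estimate feeds Interim 2, and because two programmers could build different datasets from the present text.

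**What to change.** In SAP Table 8.1:

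1. Delete *treatment and/or* from the censoring rule. Use all ordinal scores and the D28 call regardless of study treatment, and censor a treatment stopper only at last contact if lost to follow-up or withdrawn from the study.
2. State that the death rule, at risk to D15 or D28, takes precedence after a treatment stop.
3. Apply the same definition to the D28 responder indicator, so that a stopper who later responds counts as a responder in both endpoints.
4. Keep censoring at treatment stop as a named sensitivity analysis.

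Reconcile protocol 7.1.2 with SAP 4.2 on whether stopping treatment ends study participation. A hospital transfer also stops dosing ("No IMP will move with the participants and hence dosing will stop", SAP 3.6.2), but leaving the first hospital without improvement has its own censoring clause, which this change does not touch.

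The cost is a few lines of SAP text and one derivation. No new assessments are needed; scores will be available for stoppers who remain on study, and those who leave are censored as now.

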2.4 Determination of sample size

The outcome(s) on which the sample size calculation is based upon, is the primary endpoint measurement of oxygenation, defined as ratio of PaO₂/FiO₂.

The target difference is the difference from baseline measured at the primary endpoint (at day 6 and day 15) between the control and the treated group. Given a sample size of 81 participants, 54 on Zilucoplan® and standard of care and 27 on standard of care there would be >85% power to show a significant difference from standard of care at the 2 sided 5% level if the true underlying treatment difference was an 80 point difference (25% of 320, being the mean at hospital admission) in the PaO₂/FiO₂ ratio. This assumes a standard deviation of 105 and a dropout rate of less than 10%.

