3.4 Treatment assignment and treatment groups

Participants will be randomized onto one of the two treatment arms (Arm A: Zilucoplan®+SOC, Arm B: SOC only) in a 2:1 ratio. The 2:1 randomisation will be carried out using REDCap (electronic IWRS system) by centre. No other stratification factors are planned.

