4 STATISTICAL/ANALYTICAL ISSUES

4.1 Adjustments for covariates

Covariates such as sex, age, BMI (measure of obesity) and race may also be included in the models if by the time of analysis these have been identified as key differentiators in terms of COVID-19 recovery.

Weight may also be used (independently of BMI) as a covariate to explore the impact of weight on results as the usual dosing regimen for Zilucoplan® is to dose by weight.

In addition, the impact on the results of disease severity at baseline may be explored using the 4 middle categories of the 6 point ordinal scale to define disease severity at baseline as a covariate

Where indicated, some secondary endpoints will explore the impact of baseline laboratory values on efficacy endpoints eg Baseline D-Dimers and C5a values.

The addition of the interaction of any baseline covariate with treatment may be explored to identify any evidence to suggest a differential impact on results.

Prior to fitting any model, all data will be explored graphically.

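### The two sustained-response analyses in SAP Table 8.1 permit but do not pre-specify adjustment for baseline ordinal score, and the time-to-response row names no between-arm estimate

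*SAP*

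**What the plan says.** **Percentage with sustained response (SAP 8.2, Table 8.1).** The row uses PROC FREQ, or PROC LOGISTIC if covariates enter: "Model: Response=ACTARM +covariates (if added". The outputs are the response percentage per arm and an odds ratio with 95% CI. No covariate is named.

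**Time to sustained response (same table).** "Kaplan-Meier analysis using PROC LIFETEST. Strata ACTARM", with a failure plot and whatever statistics the mock shell lists. That shell is not among the documents. Deaths are set to D15 or D28 and censored there. The dataset may carry further variables for use as covariates at the final analysis.

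**Covariates in general (SAP 4.1).** "the impact on the results of disease severity at baseline may be explored using the 4 middle categories of the 6 point ordinal scale".

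**Randomisation (SAP 3.4).** 2:1 by centre; "No other stratification factors are planned".

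**Other rows on the same scale (Table 8.1).** The change-from-baseline MMRM includes baseline score and its interaction with day. The AUEC analysis includes baseline score as a covariate.

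**Reporting rule (SAP 3.1).** Secondary objectives get no p-values; comparisons of interest get 95% confidence limits.

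**The concern.** Baseline score is part of the definition of response. On the 6-point scale, a patient at 4 must reach 6 (out of hospital), a patient at 3 must reach 5 (in hospital, off oxygen), and a patient at 2 must reach 4 (low-flow oxygen). A patient at 5 cannot gain two points and can respond only by discharge. One label covers four hurdles, and nothing in the randomisation balances them across 54 and 27 patients.

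The SAP fixes baseline score in two analyses of this scale but leaves it optional in the two response rows. The trial is open-label, and the response endpoints are analysed at Interim 2, possibly also at Interim 1 (SAP 4.4). Whether to adjust, and for what, could therefore be decided after arm-level results are known.

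The time row has a separate gap. SAP 3.1 excludes p-values for secondary objectives, so a log-rank test would not be reported. The SAP text puts no hazard ratio, difference or other contrast in its place.

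**Working it through.** **1. The plan's own figure.** The only stated power concerns the primary PaO₂/FiO₂ comparison: ">85% power to show a significant difference" "at the 2 sided 5% level", with difference 80, SD 105, 54 vs 27 and dropout below 10% (SAP 2.4).
- SE = 105 × √(1/54 + 1/27) = 24.75; 80/24.75 = 3.23; power = Φ(3.23 − 1.96) = 89.8%.
- After 10% dropout (48.6 vs 24.3): 86.6% (noncentral t 85.7%).

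The figure reproduces and is not affected by this point. No power, response rate or hazard ratio is stated for the response endpoints.

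**2. Precision of the risk difference, by formula.** Let w be the share of patients at each baseline score and p the control response by D28. Then m = Σwp, R² = Σw(p − m)² / [m(1 − m)], and adjustment multiplies the variance of the risk difference by about 1 − R². All w and p below are assumptions, in score order 5/4/3/2.

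| Link | w (%) | p (%) | m | R² | 95% half-width, points | Equivalent N, 81/(1 − R²) |
|---|---|---|---|---|---|---|
| Weak | 5/60/25/10 | 85/75/65/55 | 0.710 | 0.026 | 21.0 → 20.7 | 83 |
| Moderate | 5/55/30/10 | 90/80/55/30 | 0.680 | 0.137 | 21.6 → 20.0 | 94 |
| Strong | 5/45/35/15 | 95/85/50/15 | 0.628 | 0.288 | 22.3 → 18.8 | 114 |

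Moderate row in full:
- Σw(p − m)² = 0.05×0.22² + 0.55×0.12² + 0.30×0.13² + 0.10×0.38² = 0.0299.
- m(1 − m) = 0.2176, so R² = 0.0299/0.2176 = 0.137.
- Half-width = 1.96 × √(0.2176 × (1/54 + 1/27)) = 0.216; multiplied by √0.863 this gives 0.200.

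**3. Simulation of the same cases.** 3,000 trials each, 54 vs 27, linear baseline score, Wald tests; conditional OR 3 or HR 1.8.

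| Link | SD of risk difference | SE of log OR | Logistic power | SE of log HR | Cox power |
|---|---|---|---|---|---|
| Weak | 0.098 → 0.098 | 0.61 → 0.63 | 42 → 44% | 0.273 → 0.275 | 54 → 57% |
| Moderate | 0.102 → 0.096 | 0.57 → 0.63 | 42 → 44% | 0.279 → 0.283 | 44 → 54% |
| Strong | 0.106 → 0.092 | 0.53 → 0.65 | 33 → 41% | 0.289 → 0.296 | 30 → 47% |

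Under no effect, rejection was 4-5% with and without adjustment.

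**4. A further scenario.** Scores 2/3/4/5 in 15/40/35/10%, control response 30/60/85/95%.
- R² = 0.0416/0.2185 = 0.19, so the formula gives an SE lower by 1 − √0.81 = 10%.
- Simulated SD of the risk difference: 0.109 → 0.098 (null), 0.102 → 0.095 (OR 2.5), 0.100 → 0.093 (OR 4), a fall of 7-10%.
- Power over repeated runs: 29-31% → 34-36% at OR 2.5, and 51-54% → 60-62% at OR 4.
- SE of the log odds ratio rises: 0.51 → 0.58, 0.55 → 0.63 and 0.59 → 0.68.

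**5. Chance imbalance.** If 40% of patients are at scores 2-3, the arms differ by 15 points or more in about 17% of trials of this size.

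**6. Sparse categories.** In the step 4 mix, 27 controls split as 27 × 0.15/0.40/0.35/0.10 = 4/11/9/3. About 61% of trials have a control category with two patients or fewer. With 14 controls at Interim 1 (42/3), about 77% have one with one or none.

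**The case against.** Several stronger readings are tempting, and the documents do not support them.

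- **That the response rows ignore baseline score.** SAP 4.1 names this covariate and Table 8.1 leaves room for it. The defect is only that it is not fixed in advance.
- **That no treatment effect is planned for time to response.** The SAP text names none, but output is deferred to a shell we cannot see, and SAP 3.1 promises limits on comparisons of interest, not on every row. The related percentage row already has an odds ratio with 95% CI.
- **That adjustment narrows the planned interval.** It does not. The adjusted odds ratio is a conditional quantity, further from 1 and with a larger standard error. The Cox standard error also rises slightly; its power gain comes from the estimate moving away from the null. A narrower interval appears only for a standardised risk difference, which the SAP does not plan.
- **That the unadjusted comparison is invalid.** Randomisation protects it, and its type I error holds.
- **That response is the main clinical readout at both interims.** At Interim 1 it is optional (SAP 4.4.1). Protocol V6.0 keeps time to response as secondary (4.2) but lists the percentage endpoint as exploratory (4.3). The SAP, based on V3.0, lists both as secondary.

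Power is also an imperfect yardstick where no p-values will be reported. And a Cox model stratified on all four baseline categories would be fragile in a trial this small. All of these limits stand. What remains is the uncommitted covariate and the unnamed contrast.

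**Conclusion.** The point holds in this limited form. Two rows on the ordinal scale fix baseline score and the two response rows do not, although the score sets the hurdle for response and is not balanced by design. The time row names no contrast in the SAP text.

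The size depends on how prognostic baseline score is, which the documents do not say. For the standard error of a standardised risk difference, the reduction is about 0-1% with a weak link, 5-10% in the intermediate scenarios and 14-15% with a strong link (R² up to 0.29). Logistic power rises by 2-9 points across the scenarios and runs, and Cox power by 3-17 points. The precision gain does not extend to the odds ratio.

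This is a proof-of-concept trial with estimation-only secondary endpoints, so the priority is low to moderate. The firmer argument is removal of discretion in an open-label trial; the precision gain is a conditional benefit.

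**What to change.** In SAP Table 8.1, before Interim 2:

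1. **Both rows:** pre-specify baseline ordinal score, either as a linear term or with sparse categories combined by a rule fixed in advance.
2. **Percentage row:** report a standardised (marginal) risk difference with 95% CI beside the odds ratio. State that the adjusted odds ratio is conditional and that its interval will be wider than the unadjusted one.
3. **Time row:** keep the Kaplan-Meier curves and add a Cox hazard ratio with 95% CI, adjusted for baseline score or stratified on the combined categories. Keep deaths censored at D15/D28 as already derived. State that this estimate is also conditional.
4. **Mock shell:** if it already names a contrast, move that contrast into the SAP text.

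The cost is two model statements and one standardisation step. Baseline score is already used in neighbouring rows, so no new data are needed.
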